Study Duration and Dates	The duration of this study is expected to be approximately 18 months (10-month subject recruitment, up to 3 week screening phase, and 5-month treatment), with subject recruitment to start in May 2014 and the last subject to finish in October 2015.	Phase	IV (Open label Cycloset added to usual diabetes treatment)

Objectives

Primary Objective:

To examine the effect of the addition of Cycloset upon glucose metabolism (glycemic control including post prandial glucose metabolism) in individuals with inadequately controlled (HbA1c 7.5-10.0) type 2 diabetes (T2DM) who are already on Bydureon (exenatide once weekly) or Victoza (liraglutide once daily) as part of their standard care.

Secondary Objectives:

Since Cycloset has been shown to reduce cardiovascular events in those over the age of 18 with T2DM, we will also perform mechanistic studies evaluating for potential mechanisms for this cardiovascular benefit including non-invasive tests for the assessment of the effects of Cycloset therapy on endothelial function, aortic compliance, body weight composition, and inflammatory and oxidative stress markers.

Study Design

This is a single-site, prospective, cohort study that will assess the effect of Cycloset as add-on therapy in adult subjects with T2DM that is inadequately controlled (HbA1c 7.5% to 10.0%) on GLP-1 analog therapy with either exenatide (Bydureon) once weekly or liraglutide (Victoza) once

daily.

Entry criteria will be checked at the screening visit. All qualified subjects will undergo baseline studies including non-invasive hemodynamic testing for assessment of aortic stiffness and pulse wave velocity, assessment of body weight composition by dual-energy X-ray absorptiometry (DXA), assessment of endothelial function using the Endo-PAT device, measurement of cytokines and inflammatory biomarkers in the peripheral blood and urine, assessment of oxidative stress and inflammatory markers in white blood cells isolated from a peripheral whole blood sample, a 5-hour mixed meal tolerance test (MMT) for assessment of postprandial glucose metabolism and 24-hour ambulatory BP monitoring.

Following completion of all the baseline studies as above, subjects will be started on Cycloset, 0.8 mg/day in addition to their stable dose of Bydureon (exenatide) (2mg/week) or Victoza (liraglutide) (1.2-1.8 mg/day), and the dose will be increased by 0.8 mg/day every week to a maximum of 3.2 mg/day, or as tolerated to a minimum of 2.4 mg/day.

Subjects will return at months 1, 2, 3, and 4 for interim medical history, body weight, HbA1c, and FPG. Postural blood pressure measurements will be obtained with the subject lying down and then after standing for 5 minutes at each of the visits. At month 4, all of the baseline studies detailed above will be repeated.

All tests will be performed in the Clinical Research Center at the Texas Diabetes Institute/University of Texas Health Science Center, San Antonio.

Number Of Subjects

Planned enrollment = 15

Primary Subject Characteristics at Enrollment

T2DM male or female subjects between the ages of 30 and 70 years with HbA1c between 7.5-10% on a diabetes therapeutic regimen consisting of stable doses of either exenatide (2 mg/week) or liraglutide (1.2-1.8 mg/day) for at least 90 days prior to enrollment with or without metformin and/or pioglitazone and no other glucose lowering agents.

Study Treatments

Cycloset, 0.8 mg/day, with the dose increased by 0.8 mg/day every week to a maximum of 3.2 mg/day, or as tolerated to a minimum dose of 2.4 mg/day, added on to usual diabetes therapy consisting of a stable dose for at least 90 days of exenatide (2mg/week) or liraglutide (1.2-1.8 mg/day). Subjects must be on either exenatide or liraglutide as part of their standard care to be eligible for study participation.

Study Endpoints

The primary endpoint is the effect of Cycloset on glycemic control and postprandial glucose metabolism.

Secondary endpoints include the effects of Cycloset on endothelial function, aortic compliance,, body weight composition, blood pressure and markers of inflammation and oxidative stress.

Statistical Procedures

Sample Size Calculation: Assuming that Cycloset will cause a 0.6% reduction in HbA1c, we computed that 15 subjects provide 90% power to detect a 0.6% decrease from a baseline HbA1c of $8.0 \pm 0.5\%$ at an alpha of 0.05.

A statistical analysis plan (SAP), providing details of the analyses and presentation structure of the results, will be developed and finalized before the database is locked.

STUDY SCHEDULE

	Screening Period					Treatment Period (16 weeks)						
Data collected and/or action	Visit 0*	Visit 1*	Visit 2	Visit 3	Phone call 1	Phone call 2	Phone call 3	Visit 4	Visit 5	Visit 6	End of Study Visit 7 ^α	End of Study Visit 8 ^α
	Week -3 to -1	Week 0 (baseline)	Visit 1 +7-10 days	Visit 2 +3-5 days	Day 7	Day 14	Day 21	1 Month	2 Months	3 Months	4 Months	Visit 7 +3-5 days
Informed Consent	Х											
Entry Criteria	X		Х									
Medical History	Х							Х	Х	Х	Х	
Physical Exam	Х											
Body Weight	Х		Х					Х	Х	Х	Х	
ECĞ	Х											
Hematology and chemistry	Х										Х	
Lipids	Х										Х	Х
HbA1c	X							Х	Х	Х	X	X
Fasting plasma glucose	Х							Х	Х	Х	Х	Х
Postural Blood Pressure								X	X	X	X*	
Aortic compliance testing		Х										X*
DXA for body composition measurements				X							Х	
Assessment of endothelial function using Endo-PAT			X ¹								X ¹	
Blood sample for measurement of inflammatory biomarkers and isolation of WBCs				Х								Х
Mixed Meal Tolerance test			Х								Х	
Ambulatory BP monitoring device set up			X	Return ABPM device							X	Return ABPM device
24-hour urine collection instruction			Х	Return 24 hour urine							Х	Return 24 hour urine
Cycloset Titration				X (first dose same day as visit 3)	х	х	х					Discontinue Cycloset
Concomitant meds	To be assessed throughout the study											
Adverse Events	To be assessed throughout the study											
Hypoglycemia	To be assessed throughout the study											
Serious Adverse Events	To be assessed throughout the study Report serious adverse events to sponsor within 24 hours											
Mandatory Contact	Weekly titration phone contacts as described in the protocol											

Endo-PAT conducted upon arrival to study site and at 90 minutes into the Mixed Meal Tolerance test

* These tests (DXA and Aortic compliance testing) may be done on either Visit 7 or Visit 8

Mixed MEAL TOLERANCE TEST

		3-3H-Glu/					
Time	Glucose		C-pep/Ins	Glucagon	FFA	GLP-	1/GIP
(minutes)	(0.5 ml)	(6 ml)	(3 ml)	(2 ml)	(2 ml)	(3 ml) (2 ml)
-180	X	X	X	X	X	X	
-180	start 3-3H-glud	ose					
-30	Χ	X*					
-20	Χ	X*	Χ	X	Χ		Χ
-10	X	X*	Χ	X	Χ		Χ
-5		X*					
0	X	X*	Χ	X	Χ		ХХ
0	Mixed meal with 1-1-glucose	4C-					
15	X	X	Χ				
30	X	X	Χ	X	Χ		
45	X	X	Χ				
60	X	X	Χ	X	Χ		Χ
75	X	X	Χ				
90	X	X	Χ	X	Χ		
105	X	X	Χ				
120	X	X	Χ	X	Χ		Χ
135	X	X					
150	X	X	Χ	X	Χ		
165	X	X					
180	X	X	Χ	X	Χ		
195	X	X					
210	X	X	Χ	X	Χ		
225	X	X					
240	X	X	Χ	X	Χ		Χ
255	X	X	Χ	X	Χ		
270	Χ	X	X	X	Χ		
285	X	X	X	Χ	X		
300	Χ	X	X	X	Χ		
Number	26	26	21	16	16	3	5
Blood volume (ml)	13	156	63	32	32	9	10

Total blood loss (ml) = 315 ml

^{* 3-3}H-glucose only

ABBREVIATIONS AND DEFINITIONS

ABPM Ambulatory Blood Pressure Monitoring

AE Adverse Event

BG Blood Glucose

BMI Body Mass Index

CRC Clinical Research Center

CRF Case Report Form

DM Diabetes Mellitus

FPG Fasting Plasma Glucose

GCP Good Clinical Practice

GLP-1 glucagon-like peptide

HbA1c Hemoglobin A1C

ICH International Conference on Harmonization

IEC Independent Ethics Committee

IRB Institutional Review Board

IV Intravenous

MMT Mixed Meal Tolerance test

SAE Serious Adverse Event

SAP Statistical Analysis Plan

SMBG Self-Monitored Blood Glucose

T2DM Type 2 diabetes mellitus

VS Vital Signs

1 INTRODUCTION AND STUDY RATIONALE

A. Summary

Type 2 diabetes mellitus (T2DM) is a common metabolic cardiovascular disorder characterized by multiple pathophysiologic abnormalities (1). Quick release bromocriptine (Cycloset), a D2-dopamine receptor agonist sympatholytic agent, was approved by the U.S. Food and Drug Administration in 2009 for use as monotherapy and in combination with oral antidiabetic agents for the treatment of T2DM (2) in those with T2DM over the age of 18. In humans, Cycloset reduces the postprandial glucose excursion without augmenting insulin secretion or improving insulin sensitivity in muscle (3,4). These results suggest that Cycloset enhances hepatic sensitivity to insulin, perhaps by inhibiting central sympathetic outflow, and are consistent with results obtained in rodents (5).

The glucagon-like peptide (GLP)-1 receptor agonists, liraglutide and exenatide, also reduce postprandial, as well as fasting, hyperglycemia following glucose ingestion (6,7). The reduction in postprandial hyperglycemia results from a delay in gastric emptying and enhanced suppression of hepatic glucose production secondary to increased insulin secretion and decreased glucagon secretion (6,8). To date, no study in man has examined combination therapy with a GLP-1 receptor agonist and Cycloset. Since both agents work by reducing postprandial hyperglycemia and inhibiting post-meal HGP, although by different mechanisms, one might expect them to have an additive or even synergistic effect to reduce postprandial plasma glucose levels. In fact, a synergistic interaction between bromocriptine and exenatide has been demonstrated in the glucose intolerant, insulin resistant Syrian hamster (9).

In the present study we will examine the effect of the addition of Cycloset therapy to inadequately controlled (HbA1c 7.5-10.0) T2DM patients on exenatide (Bydureon) once weekly or liraglutide (Victoza). Since Cycloset has been shown to reduce cardiovascular events in adults with T2DM (10), a beneficial effect that maybe associated with improved endothelial/vascular function, we also will measure endothelial function using the Endo-PAT instrument and assess aortic compliance using non-invasive hemodynamic testing.

- 1. DeFronzo RA. Banting Lecture: From the triumvirate to the ominous octet: a new paradigm for the treatment of type 2 diabetes mellitus. Diabetes 58:773-95, 2009.


B. Detailed Background

Cycloset is a dopamine receptor agonist indicated as an adjunct to diet and exercise to improve glycemic control in adults with type 2 diabetes mellitus (T2DM). Cycloset reduces glucose following each meal without raising plasma insulin levels. As such, Cycloset may be acting as a postprandial insulin sensitizer and/or glucose regulator (Pijl et al 2000) to reduce postprandial hyperglycemia and may be expected to synergize with incretin mimetics that increase postprandial insulin levels.

Available evidence indicates that Cycloset improves glycemic control in patients with type 2 diabetes predominantly by improving postprandial responsiveness to insulin. Once daily morning Cycloset therapy increases insulin-stimulated glucose disposal as assessed by the euglycemic insulin clamp technique and it also reduces post load glucose levels following an oral glucose tolerance test without increasing plasma insulin levels in type 2 diabetes subjects (Pijl et al 2000). The selective effect of timed bromocriptine treatment on postprandial versus post-absorptive glucose metabolism is exemplified by its much more pronounced effect on glucose clearance during a hyperglycemic versus euglycemic insulin clamp (Ezrokhi et al, 2008).

In clinical studies, Cycloset therapy has been shown to reduce postprandial glucose levels across the three standard meals of the day without increasing plasma insulin levels when used alone or in combination with sulfonylurea therapy (Cincotta et al, 1999). Among patients with type 2 diabetes failing sulfonylurea therapy (two identically designed studies with; n= 494; baseline HbA1c of 9,3), the addition of Cycloset as compared to placebo resulted in reductions in post prandial glucose after 24 weeks of treatment (Cincotta 1999).

Post prandial glucose exursions contribute to the excessive morbidity associated with type 2 diabetes (Ceriello, 2008). The mechanism by which timed Cycloset elicits its postprandial glucose metabolism effect is believed to involve its ability to normalize aberrant fuel sensing neurons in the hypothalamus that inappropriately induce insulin resistance respecting regulation of hepatic glucose output, adipose lipolysis, and glucose disposal in liver and muscle. Under normal conditions, in response to a meal, fuel sensing neurons in the hypothalamus act via the neuroendocrine axis to improve insulin sensitivity in liver, adipose, and muscle after a meal to reduce hepatic glucose output and adipose lipolysis, and to increase glucose disposal in liver and muscle. However, in insulin resistant states like T2DM, this fuel sensing mechanism is altered and no longer sends these meal-induced insulin sensitizing signals to the periphery but

rathersends signals that tend to oppose insulin action, and postprandial dysglycemia ensues (Cincotta 2002, Luo et al 2008).

One of the actions of the incretin mimetics such as the GLP-1 analogs is to stimulate postprandial beta cell insulin secretory response to plasma glucose (see drug labeling information; www.fda.gov). Thus the combination of Cycloset that is working as a post prandial insulin senstizier with therapies that increase post prandial insulin would be expected to provide complimentary glucose lowering effects. As described above, Cycloset has been shown to reduce postprandial glucose levels when used in combination with insulin secretagoues. In animal models of insulin resistance, the combination of bromocriptine and a GLP-1 analog was shown to work synergistically to improve glycemic control. The interactive effect of chronic (2) week) bromocriptine treatment on glucose tolerant/insulin resistant animals that were administered a GLP-1 analog just prior to the glucose tolerance test (GTT) was assessed in a 2 week study. Intraperitoneal administered bromocriptine or vehicle was administered daily for 2 weeks at the onset of locomotor activity. A GTT was performed on all animals on day 13. On the day of the GTT, each of the BC and vehicle groups was divided in half and administered either vehicle or Exendin 4 just prior to the initiation of the GTT. The combination of timed bromocriptine plus a GLP-1 analog produced marked improvement in the GTT of severely glucose intolerant hamsters, to an extent much greater than the sum of either therapy (Ezrokhi 2012).

Therefore, both a mechanistic rationale and empirical experimental evidence implicate a beneficial interaction between bromocriptine and the incretin mimetics (GLP-1 analogs) upon postprandial hyperglycemia in insulin resistant states. To date, however, no such studies investigating the interactive effects of a GLP-1 analog and Bromocriptine-QR (Cycloset) have been conducted in humans..

2 STUDY OBJECTIVES

2.1 PRIMARY OBJECTIVE

The objective of this study is to examine the effect of the addition of Cycloset on glycemic control in inadequately controlled (HbA1c 7.5-10.0) T2DM patients who are already on Bydureon (exenatide once weekly) or Victoza (liraglutide) as part of their standard care.

An additional co-primary objective of the study is to examine the effect of Cycloset on postprandial glucose metabolism.

2.2 SECONDARY OBJECTIVES

Secondary Efficacy

To assess the potential beneficial effect of Cycloset on endothelial function, arterial stiffness, body weight composition, blood pressure, inflammation and oxidative stress.

Safety

The safety objectives of this study are to investigate the relative differences from baseline to end of study in:

- · Occurrence of hypoglycemia
- Adverse events
- Laboratory values: standard blood chemistry and hematology
- Clinical values: physical examination, vital signs and weight.

3 STUDY DESIGN, DURATION AND DATES

3.1 STUDY DESIGN

This is a single center prospective cohort study that will assess the effect of Cycloset in in T2DM subjects who are inadequately controlled (HbA1c 7.5% to 10.0%) on GLP-1 analog therapy with either Bydureon (exenatide once weekly) or Victoza (liraglutide).

Subjects who meet the entry criteria will first undergo non-invasive hemodynamic testing for a baseline assessment of aortic compliance (Visit 1). Subjects will then come to the Clinical Research Center (CRC) at the Texas Diabetes Institute on the morning of Visit 2 following a 10-12 hour overnight fast and restriction from use of caffeine, tobacco, vitamins or medications that might affect vascular tone. Subjects will take their normal dose of exenatide or liraglutide in the

morning prior to this visit. At this visit, subjects will a non-invasive assessment of endothelial function using the Endo-PAT 2000 device Subjects will then receive a 5-hour MMT test. At approximately 90 minutes into the completion of the MMT test, a second Endo-PAT recording will be conducted. Upon completion of the second Endo-PAT test, subjects will be placed on a continuous ambulatory BP monitor and asked to collect a 24 hour urine sample, which they will start the following morning. After completion of the 24-hour urine collection, subjects will return to the CRC for Visit 3. At this visit, the ambulatory BP data will be downloaded and the 24-hr urine sample will be stored. Subjects will also have a DXA scan performed for assessment of body weight composition and have blood samples drawn for the measurement of serum cytokines and inflammatory biomarkers and isolation of white blood cells at this visit.

At Visit 3 subjects will be started on Cycloset, 0.8 mg/day in addition to their stable dose of Bydureon (exenatide) (2mg/week) or Victoza (liraglutide) (1.2-1.8 mg/day). Subjects will receive their first dose of Cycloset in the CRC and will be monitored for one hour after the dose before being sent home. The Cycloset dose will then be increased by 0.8 mg/day every week to a maximum of 3.2 mg/day, or as tolerated to a minimum of 2.4 mg/day. During the Cycloset titration phase subjects will be monitored by phone with weekly phone visits. Subjects who cannot tolerate at least 2.4 mg/day of Cycloset will be replaced.

Subjects will return at months 1, 2, 3, (Visits 4, 5 and 6) for interim medical history, body weight, HbA1c, and FPG. At month 4 (End of Study Visits 7 and 8), all of the tests performed at Baseline Visits 1-3, including non-invasive hemodynamic testing for assessment of aortic compliance, DXA for assessment of body weight composition, Endo-PAT tests for assessment of endothelial function, MMT test, collection of blood samples for measurement of inflammatory/ oxidative stress markers and isolation of white blood cells, 24-hour ambulatory BP recording and collection of a 24-hour urine sample will be repeated as described above. Cycloset administration will be discontinued at the completion of Visit 8.

Two weeks after Cycloset administration is discontinued subjects will return for Visit 10 and complete a final assessment of aortic compliance. There will be no additional follow up after Visit 10.

STUDY PROCEDURES

Endo-PAT

The Endo-PAT 2000 is a device that is used to assess endothelial vasodilator function in a rapid and non-invasive fashion. The device consist of two plethysmographic probes that are placed on the index finger of each hand and record endothelium-mediated changes in the digital pulse waveform known as the PAT (Peripheral Arterial Tone) signal. Blood pressure cuff is then inflated to induce downstream peripheral hyperemia by occluding blood flow through the brachial artery for 5 minutes. The contra-lateral arm is used as a control. Endothelium-mediated changes in the PAT signal are elicited by creating a downstream hyperemic response.

Briefly, the Endo-PAT measurements will be taken in a fasting state and be conducted in a quiet, dimly lit, temperature-controlled exam room to reduce fluctuations in vascular tone. The patient will remain supine and comfortable for 15 minutes so as to attain a cardiovascular steady-state with two arm-supporters along each of the patient's sides to support the patient's arm. The index

finger will be used to place Endo-PAT probe for the study; however, if this finger is unsuitable, a different digit (except the thumb) may be used, as long as the same finger is used on both hands. Blood pressure will be measured using the control arm (the arm that is not occluded during the Endo-PAT study. A second blood pressure cuff will be placed on the arm to be occluded during the Endo-PAT study. The Endo-PAT device will be employed and the blood pressure cuff will be inflated at that time. During the procedure the patient will be asked to refrain from moving the fingers, as this will create mechanical artifacts. It is important for the patient to be relaxed throughout the study. During the test and while the arm cuff is inflated, subjects may feel some discomfort, numbness, or tingling. In case of incomplete occlusion the cuff may be inflated to a maximum of 300 mmHg. The measurement will be taken for 5 minutes. During that time, the blood pressure cuff will be rapidly inflated to a supra-systolic pressure of 60 mmHg above the patient's systolic pressure or 200 mmHg, whichever is higher. The complete cessation of blood flow to the hand is verified by the absence of a PAT signal from the occluded arm. After 5 minutes occlusion, the cuff will be released as quickly as possible and a five-minute post occlusion measurements will be recorded.

The Endo-PAT system calculates the response to reactive hyperemia and a PAT ratio is created using the post and pre occlusion values. These values are normalized to measurements from the contra-lateral arm, which serves as control for non-endothelial dependent systemic effects. The technique provides values for the calculation of a Reactive Hyperemia Index (RHI), which gives an indication of the endothelial vasodilator function. The RHI, in turn, correlates with the measurement of endothelial vasodilator function in the coronary arteries and thus predicts the potential unfavorable cardiovascular conditions and outcomes.

Noninvasive Hemodynamic Assessment_of Aortic Compliance

Subjects will be rested in the supine position for 15 minutes. Measurements for the assessment of aortic pulse wave velocity (PWV) will then be taken immediately after measurement of brachial blood pressure. PWV is determined by simultaneous measurement of arterial pressure waves at the carotid and femoral arteries with sensitive pressure transducers place on the skin overlying the carotid and femoral arteries. This is a completely noninvasive procedure using previously described and published techniques (Circulation 2006; 113: 1213-1225). The surface distance from suprasternal notch to the distal (femoral) recording site is measured, and the pressure wave transit time is calculated using a foot-of-the-wave to foot- of-the-wave method. PWV is calculated by dividing the distance to the distal site by the pressure wave transit time. Data are collected by a single trained observer, and the mean of at least 2 PWV measurements is taken for each subject.

Meal Tolerance Test (MMT)

Following a 10-12 hour overnight fast, catheters will be placed in the antecubital vein or hand vein, one for infusion of tritiated glucose and one for blood withdrawal. At -180 minutes baseline blood samples (see attached flow sheet) will be obtained and a prime (40 uCi x FPG/100) – continuous (0.40 uCi/min) will be started. Blood samples for determination of plasma, glucose, insulin, C-peptide, glucagon, FFA, glucagon-like peptide-1, and glucose-dependent insulinotropic polypeptide and tritiated glucose and 14C-glucose radioactivity will be obtained at -180, -30, -20, -10, and 0 minutes. At time zero subjects will ingest a mixed meal (75 grams of glucose, 25 grams of fat, 20 grams of protein, 600 kcal) over 15-20 minutes. The glucose will be labeled with

100 uCi of 1-14C-glucose. Plasma samples for substrates, hormones, and radioactivity will be obtained every 15 minutes for 5 hours. Plasma samples for catecholamines (CA) will be collected at -10, 0, 60, 120, and 240 minutes.

Meal tolerance will be determined by calculating the glucose AUC (trapezoidal rule) during the MTT. Insulin secretion will be calculated as I0-300/G0-300, CP0-300/G0-300, and ISR0-300/G0-300, where ISR = insulin secretary rate (deconvolution of the plasma C-peptide curve). Beta cell function (11) will be calculated as the insulin secretion/insulin resistance (disposition) index: ISR0-300/G0-300 x Matsuda Index of insulin sensitivity (12). The same measures will be examined for the following time intervals: -10, 0, 0-60, 0-120, 0-180, and 0-240.

During the fasting postabsorptive state, the rate of HGP equals the rate of glucose uptake by all tissues in the body and is calculated as the tritiated glucose infusion rate (DPM/min) divided by the plasma tritiated glucose specific activity (DPM/mg). Following meal ingestion, non-steady state conditions prevail and the rates of total (RaT) and oral (RaO) glucose appearance in the systemic circulation are calculated using Steele's equation from the 14C-glucose and 3H-glucose specific activities, respectively, as previously described (13). The difference between RaT and RaO yields the rate of endogenous HGP. Subtraction of RaO from 75 grams (ingested glucose load) gives the splanchnic (primarily reflects) glucose uptake.

Dual-Energy X-ray Absorptiometry (DXA)

After an overnight fast, a DXA scan for body composition scan will be performed using a Hologic DXA scanner. Subjects will be resting comfortably in supine position in a quiet room and the entire body will be scanned. The acquired images will be integrated and analyzed by a software IBM computer program and total amount of fat and fat-free mass and total body water will be estimated. Total and regional fat and fat-free mass will be measured by a licensed radiology technician using a Discovery 010-1596 instrument from Hologic that is housed on the CRC at the Texas Diabetes Institute.

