7.2.2.3 Baseline – Visit 3 (Visit 2 + 3-5 days)

- ABPM device will be returned and data downloaded.
- 24 hour urine collection will be returned
- DXA for body composition will be conducted
- Bloods for inflammatory markers and white blood cell isolation. Total amount of blood drawn at this visit will be approximately 20 ml.
- First dose of Cycloset will be administered in the CRC with a one hour post dose observation period
- Instructions for titration of Cycloset will be reviewed.

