7.2.3.1 Visit 7 (Month 4) \pm 3 days

- Subjects will arrive in the morning after an overnight fast (defined as no caloric intake for 10-12 hours)
- Assessment for any AE/SAE will be completed
- Medical history and weight will be taken
- Postural blood pressure measurements will be obtained first with the subject lying down and then repeated after 5 minutes of standing
- Assessment of aortic compliance may be conducted at this visit or on a separate day
- DXA for body composition will be conducted
- 5-hour Mixed Meal Tolerance test (MMT) will be conducted.
- Endo-PAT will be performed t0 and t90 of meal tolerance test
- Blood samples will be drawn for lipids, HbA1c and fasting glucose
- lood samples will also be drawn at various time points as part of the MMT test as detailed in the Study Design section and Study Schedule table above. Total amount of blood drawn at this visit will be approximately 350 ml.

Ambulatory Blood Pressure Monitoring (ABPM) device will be set up

7.2.3.2 24 hour urine collection instructions will be given Visit 8 (Visit 7+ 3-5 days)

- Subjects will arrive in the morning after an overnight fast (defined as no caloric intake for 10-12 hours)
- Assessment for any AE/SAE will be completed
- Assessment of aortic compliance will be conducted if not done at Visit 7
- Blood samples will be drawn for lipids, HbA1c and fasting glucose.
- ABPM device will be returned and data downloaded.
- 24 hour urine collection will be returned
- DXA for body composition will be conducted if not done at Visit 7.
- Bloods for inflammatory markers and white blood cell isolation. Total amount of blood drawn at this visit will be approximately 20 ml.
- Cycloset will be discontinued

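### The 24-hour urine is held 1 to 3 days before hand-in, and the holding time can differ between baseline and month 4; ending the collection on arrival removes this

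*Combined protocol and SAP*

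**What the plan says.** **Start of collection.** Section 3.1 has subjects leave Visit 2 with an ambulatory blood pressure monitor and "asked to collect a 24 hour urine sample, which they will start the following morning".

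**Return and storage.** The same section continues: "After completion of the 24-hour urine collection, subjects will return to the CRC for Visit 3". At that visit "the ambulatory BP data will be downloaded and the 24-hr urine sample will be stored".

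**Timing of the return visit.** The heading of section 7.2.2.3 reads "Visit 3 (Visit 2 + 3-5 days", and one of its items is "24 hour urine collection will be returned". The Study Schedule table gives the same interval.

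**Month 4.** Section 3.1 says "collection of a 24-hour urine sample will be repeated as described above". The return visit has the same window: "Visit 8 (Visit 7+ 3-5 days" (heading of section 7.2.3.2). The urine is handed in at that visit.

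**Purpose.** The Study Design entry of the Protocol Outline lists "measurement of cytokines and inflammatory biomarkers in the peripheral blood and urine". Section 7.3.2 makes inflammatory and oxidative-stress markers secondary efficacy data, read as change from baseline.

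**Handling.** Section 7.2.2.2 and the end of section 7.2.3.1 (where the line has run into the next heading) say only that collection instructions are given, without a start time. Section 7.3 refers to standardized guidelines for blood and urine specimens but does not reproduce them. No section describes an earlier drop-off, a storage condition away from the site, or a maximum holding time.

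**The concern.** Read alone, section 3.1 describes a natural sequence: finish the collection, then come back. The 3-to-5-day window rules out a return on the day the collection ends, so at least one day of holding is built in. The length of that holding depends on where in the window the visit is booked, separately at baseline and at month 4.

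The endpoint is a within-subject change in 15 subjects who all receive Cycloset. If a urinary marker drifts while the sample waits, a difference in waiting time enters the subject's change score. Without a control arm, nothing in the design separates that contribution from a drug effect. What is at stake is the precision of the urinary part of one secondary endpoint. The primary endpoints and the sample size are not affected.

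**Working it through.** The plan states no holding time, so there is no figure to reproduce. The check is calendar arithmetic on the visit windows.

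**Inputs** (day 0 = Visit 2, or Visit 7 at month 4)
- Collection starts on the morning of day 1 and ends on the morning of day 2 (section 3.1).
- The return visit is on day 3, 4 or 5 (Study Schedule; sections 7.2.2.3 and 7.2.3.2).
- The procedure and window are the same at month 4 (section 3.1).

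**Step 1: holding time at each time point.** Holding time = return day − 2. Age of the first void = return day − 1.

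| Return day | Holding time of the finished sample | Age of the first void |
|---|---|---|
| 3 | 3 − 2 = 1 day | 3 − 1 = 2 days |
| 4 | 4 − 2 = 2 days | 4 − 1 = 3 days |
| 5 | 5 − 2 = 3 days | 5 − 1 = 4 days |

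**Step 2: difference within a subject.** Visit 8 holding time minus Visit 3 holding time runs from 1 − 3 = −2 to 3 − 1 = +2 days.

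**Step 3: how often it differs (assumption).** The documents do not say how visits are spread within the window. If return days are evenly spread over 3, 4 and 5 and independent at the two time points, there are 9 equally likely pairs:
- no difference: 3/9
- 1 day in either direction: 4/9
- 2 days in either direction: 2/9

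The mean difference is 0. The mean absolute difference is (4 × 1 + 2 × 2)/9 = 8/9 day. The SD is √[(4 × 1² + 2 × 2²)/9] = √(12/9) = 1.15 days.

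**Step 4: effect on the change score.** Let r be the drift of a marker per day of holding, taken as linear on the scale of analysis. The added error in one subject's change is r × (difference in days), so at most 2r. Under the assumption in step 3, its SD is 1.15r per subject. Its own contribution to the standard error of the mean change with 15 subjects is 1.15r/√15 = 0.30r. The documents give no value for r and name no urinary analyte, so this cannot be turned into a percentage. If the samples are well preserved, r may be close to zero.

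**Step 5: after moving the start.** If collection starts on the morning before the return visit (day 2, 3 or 4), it ends on the morning of that visit (day 3, 4 or 5). The holding time is 0 days at both time points, so it cannot differ. The start then falls 2 to 4 days after the meal test instead of 1.

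**Step 6: treatment status after the move.** The first Cycloset dose is given at Visit 3 (section 7.2.2.3), so the baseline sample stays before treatment if it is complete and handed in before that dose. Cycloset stops at the end of Visit 8 (section 3.1), so the final sample is still on treatment.

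**The case against.** **The specimen guidelines may already deal with this.** Section 7.3 names urine and aims at uniform data. Cooling, preservative or a holding limit could be in those guidelines or in the instructions handed to subjects. This stands: the documents show a holding time that varies by rule, not a sample that degrades. That the container stays at home is also an inference from the instruction to return it.

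**A reader might infer a biased mean change.** The documents do not support that. The window is 3 to 5 days at both time points, so a mean shift would need visits to be booked systematically differently at month 4, and no section provides for that.

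**A reader might put a figure on the harm.** Assuming a drift of 5 to 10% per day, for instance, a 2-day mismatch would give about 10 to 20% false change in one subject. That rate has no basis in the documents, and 2 days is the extreme case.

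**A reader might extend the point to all inflammatory and oxidative-stress markers.** The Protocol Outline ties urine to cytokines and inflammatory biomarkers, and places the oxidative-stress assessment in white blood cells from a blood sample. Those bloods are drawn on site at Visits 3 and 8 and do not wait.

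**A reader might add that the collection follows a day of heavy blood sampling and tracers.** That applies equally at baseline and month 4, and gives no reason for a bias in the change.

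**The change of timing has a price.** It swaps a fixed 1-day gap after the meal test for a gap of 2 to 4 days, which can itself differ between time points. Subjects must start without a same-day prompt, and a rescheduled visit could spoil the timing. This stands as a modest cost.

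**Conclusion.** The timing point holds. From the protocol's own windows, the finished urine sample is held 1 to 3 days before hand-in, and a subject's two holding times can differ by up to 2 days. This rests on reading the following morning as the day after Visit 2 (or 7) and on hand-in only at the return visit, both of which the text supports.

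The consequence is limited. It is avoidable noise in the change in urinary cytokines and inflammatory biomarkers, of a size that the documents do not allow anyone to compute. It should be treated as a cheap improvement to the collection procedure, not as a threat to the trial's main conclusions.

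**What to change.** - **Section 3.1:** replace the instruction to start the following morning with a start on the morning of the day before Visit 3 (or Visit 8), so that the collection ends on arrival.
- **Sections 7.2.2.2 and 7.2.3.1:** insert the same timing. There is no start time to replace there.
- **Section 7.2.2.3:** state that the baseline collection is completed and handed in before the first study-drug dose.
- **Case report form:** record the end-of-collection and freezing times at both time points.

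**Cost.** A few lines of text and two recorded times, with no added visit or container; the ambulatory blood pressure timing is unaffected. The collection moves to 2 to 4 days after the meal test, and a reminder call or message the day before it starts is advisable. If a visit is moved within its window, the start should move with it.

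**Alternative.** If the sponsor prefers to keep the fixed 1-day gap, the protocol could state the storage conditions and a maximum holding time, or cite the specimen guidelines that do so, and record the hand-in time. This makes the wait visible and limits its effect, but does not make it equal at the two time points.
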